General insertion guidelines for the ENG implant recommend initiation within 5 days of last menstrual period (LMP) to avoid the risk of a luteal-phase pregnancy (LPP). Two studies provide data on risk of LPP with same-day initiation beyond 5 days after LMP. First, a retrospective study based in Colorado had pregnancy outcome data on 57% of adolescents who initiated the implant outside the guidelines. They reported a LPP rate of 0.9% (10/1066; 95% CI=0.5–1.7%), and only 8.2% of participants received same-day oral EC for recent reported unprotected intercourse (UPI). [1] A secondary analysis of the HER Salt Lake study reported pregnancy risk of same-day implant initiation in women reporting UPI within the past 14 days with and without oral EC use was 1.2% (95% CI=0.03%- 6.5%). Despite a small sample size, this group included women at high risk of pregnancy in the cycle evaluated because several reported UPI beyond the 5-day eligibility for oral EC and multiple episodes of UPI. [2] These data show a low risk of LPP in women receiving outside-of-guideline initiation, even in those reporting UPI. **Clinicians, and implant users lack robust data on pregnancy risk for the guideline-adherent, EC-eligible population desiring same-day ENG implant placement and oral EC.**

Women presenting for EC often need ongoing contraception, but clinical practice is not standardized in same-day counseling and initiation due to system-, provider-, and client-level barriers. Understanding the interest in same-day LARC initiation would help interventions to overcome these barriers, but data are again limited on this topic. One retrospective chart review from 2011-2013 reported on an intervention to offer comprehensive contraceptive counseling at the time of EC encounters. The authors found increased uptake of all LARC methods from zero women initiating the same day as EC prior to intervention and 12% (38/328) with same-day initiation during the intervention (33 copper IUDs, 3 LNG IUDs, and 2 ENG implants). At 3-month follow-up, 10% of women had initiated a LARC method prior to the intervention. This increased to 22% post-intervention. [3] Since execution of that study two important trends support the need for execution of this proposal. **Interest in LARC use continues to steadily increase as does the practice of same-day contraception initiation (quick-start). Because of these changes in user demand and provider supply, we need new estimates of interest in same-day LARC initiation at the time of EC encounters.**

Women presenting for EC may not have considered LARC options prior to the encounter and same-day initiation may impact continuation rates. A prospective observational trial assessing

same-day initiation of IUDs at time of EC encounters found one-year continuation rates of 60% in copper IUD users and 70% in LNG IUD plus oral LNG users. [4] **Data on implant continuation rates at time of same-day initiation with an EC encounter are lacking.**

The ENG implant is a synthetic progestin with a quick rise in serum levels which, in theory, could stabilize a dominant follicle and serve as EC without the addition of oral LNG. Thus, eventually we may have evidence that the ENG implant alone is sufficient for EC. However, now EC users desiring same-day implant initiation and clinicians willing to provide the service need **baseline data on pregnancy rates for guideline-adherent same-day initiation of the ENG implant with oral LNG EC. We propose to generate a baseline estimate and compare it with historical controls of oral LNG EC alone.**

Study design: Prospective observational single site clinical trial

Participant recruitment and study site: All women age 18-35 years old who present to a Planned Parenthood Association of Utah (PPAU) clinic requesting EC will receive a one-page handout offering (1) same-day method initiation with oral LNG + ENG implant or other hormonal method, (2) copper or LNG IUD alone, or (3) UPA with delayed initiation of hormonal contraception if BMI >30. Women initiating an ENG implant + oral LNG EC will be offered enrollment into a prospective observational survey study. All study procedures will occur at PPAU clinics. Standard clinical counseling at participating health centers includes differences in efficacy between oral LNG and UPA by BMI and in those between 3-5 days out from UPI. Women desiring the most effective oral method of EC will be offered ulipristal acetate.

Sample size: This is an observational trial to gain a point estimate for pregnancy rate following guideline-adherent, same-day method initiation with oral LNG + ENG implant compared to published pregnancy rates following oral LNG EC alone. [5] Our maximum sample goal is 300 women with 1-month pregnancy outcome data and the 1st 100 women will be followed for the secondary outcomes of 12-month continuation or reasons/timing of discontinuation. We will use the 2 PPAU clinics that dispense the greatest EC volume for this study (960 total EC visits in 2019) and plan to achieve our recruitment goal in 24 months. We are confident in our recruitment plan based on the 1,122 EC users receiving IUDs at these clinics who have enrolled in prospective clinical trials.

Our null hypotheses are:

- 1) ENG implant along with oral LNG EC will not have a pregnancy rate greater than published oral LNG EC (2.5%; 95%CI 1.3-4.6). [5]
- 2) Uptake of same-day ENG implants will be lower than same-day IUD uptake for EC.

Purpose and Objectives

Primary:

1. To determine a point estimate for the one-month pregnancy rate following guideline supported same-day initiation of an etonogestrel (ENG) implant plus oral levonorgestrel (LNG) emergency contraception (EC).
2. To determine the proportion of EC clients willing to initiate a same-day ENG implant with oral LNG EC compared to same-day initiation of intrauterine devices for EC.

Secondary:

- Describe the 6- and 12-month continuation rates of the ENG implant with same-day initiation at an EC encounter.
- Describe the timing and reasons for ENG implant discontinuation in the 12 months following same-day initiation at an EC encounter.

Clinical hypotheses.

- Combined oral LNG EC administration with same-day ENG implant insertion will not increase pregnancy rate point estimate compared to oral EC alone.
- EC clients willing to initiate a same-day LARC method will preferentially chose the ENG implant over IUDs and
- Clients initiating a same-day ENG implant will continue the method at the same rate as users who initiate at other encounters.

Study Population

Age of Participants: Women age 18-35

Sample Size:

At Utah:

All Centers:

Inclusion Criteria:

Healthy women, age 18-35 years, fluent in English and/or Spanish

BMI < 30 kg/m²

No known contraindication to either the ENG contraceptive implant or oral LNG EC using the CDC Medical Eligibility Criteria for Contraceptive Use 2016

Negative urine pregnancy test

Willing to abstain from further UPI in the 7 days following insertion

Know the date of their last menstrual period

Have a regular menstrual cycle (24-35 days)

Be willing to comply with the study requirements, and

Desiring to avoid pregnancy for at least 12 months.

Their current preferred phone number must be functioning at the time of study entry and will be tested prior to enrollment. We will obtain preferred mode of communication (phone, text, email) and also a contact information for a secondary person.

Exclusion Criteria:

Current pregnancy or breastfeeding

Previous use of oral EC in the current cycle

Report of UPI beyond 5 days in current cycle

Vaginal bleeding of unknown etiology

Allergy to LNG or ENG

IUD or implant in-place

History of permanent contraception through sterilization or hysterectomy

Monogamous partner with a vasectomy, or

Depo-provera injection within past 15 weeks.

Design

Study Procedures

Recruitment/Participant Identification Process:

All clients who present to selected Planned Parenthood Association of Utah clinics for Emergency Contraception (EC) will receive a single-page explanation of EC options (attached in Documents section of study application) with ongoing contraception initiation: copper or LNG IUD alone, oral LNG EC + implant or other hormonal contraception, oral LNG EC alone, or oral UPA EC alone (with or without delayed initiation of hormonal contraception).

This explanation will end with an assessment of interest in a contraceptive visit, which allows us to gather information on women who refuse the counseling and opted to only access oral

EC. This information will include: age, race/ethnicity, last menstrual period, and reason for declining counseling.

Women desiring additional information about the ENG implant will then be asked if she is interested in study participation, through a consent process managed by an IRB approved member of the study team.

Those with interest in other methods, including IUDs, will receive a contraceptive visit by PPAU clinical staff.

Informed Consent:

Description of location(s) where consent will be obtained:

Consent will be obtained in a private examination room at the clinic where the patient is receiving care.

Description of the consent process(es), including the timing of consent:

Due to the nature of this study, it may not be possible for patients to return at a later time to enroll in the study. Participants will have all questions answered prior to enrollment. The research staff are experienced in interviewing and working with this population. They will be certain to take the time needed to ensure that the patient understands the study and is consenting willingly. If the woman continues to have questions, she will be offered the opportunity to discuss the study in further detail with the PI or other medical providers with extensive experience with the clinical care of IUDs and emergency contraception.

Procedures:

Screening/enrollment Visit: Subjects interested in the ENG implant will be screened for eligibility and interest in the study. Each subject will have the study explained and, if she desires to participate, she will sign the informed consent prior to any study procedures. The screening/enrollment visit will include: review of medical, surgical and social history, medications, contraceptive use, height and weight to calculate BMI <30, and a urine pregnancy test. We will collect detailed information on menstrual cycle history, last menstrual period, cycle length over the preceding six months, and time of unprotected intercourse. This will enable us to calculate the timing of UPI relative to position in the menstrual cycle should any pregnancies occur. Finally, we will insert the ENG implant with co-administration of oral LNG EC (1.5mg po X1). Participants will be given a home pregnancy test with instructions on use at 1 month. They will also have a clinic appointment made for 1 month, in case of need for in-person urine pregnancy testing or follow-up from a positive home pregnancy test.

Women who choose an IUD: Women who choose an IUD and agree to participate in this study will be asked to sign the consent document. They will then be asked to complete a questionnaire about prior sexual activity, use of contraception, pregnancies and sexually transmitted infections. Completion of this questionnaire will be the only study procedure asked of this subgroup of participants. There will be no follow-up procedures.

One-month follow-up (Phone or in-person): Four weeks after enrollment, the research staff will contact the participant per their contact preference (text, phone, etc.) and send a link to a

RedCAP survey to record the results of their home pregnancy test, assess satisfaction with the implant and record any adverse events that have occurred. If the participant is unable to complete the home pregnancy test and record results, a clinic visit will be scheduled for a urine pregnancy test. If a patient has a positive pregnancy test, she will receive an ultrasound, a blood test for b-HCG, standard pregnancy options counseling and removal of the implant will be recommended if she opts to continue the pregnancy. Participants will receive \$40 for this follow-up.

Three-month follow-up (Online link or Phone):* Three months after enrollment, participants will receive a link to a RedCAP survey to assess satisfaction with the implant and adverse events. If the participant has discontinued the method, we will collect the date of discontinuation, reason(s) and current contraceptive method. If the survey is not completed within 7 days, the research staff will complete up to 3 attempts to contact the participant by each contact method for survey administration. No compensation for this call.

Six-month follow-up (Online link or Phone):* Six months after enrollment, participants will receive a link to a RedCAP survey to assess satisfaction with the implant and adverse events. If the participant has discontinued the method, we will collect the date of discontinuation, reason(s) and current contraceptive method. If the survey is not completed within 7 days, the research staff will complete up to 3 attempts to contact the participant by each contact method for survey administration. Participants will receive \$20 for this follow-up.

Nine-month follow-up (Online link or Phone):* Nine months after enrollment, participants will receive a link to a RedCAP survey to assess satisfaction with the implant and adverse events. If the participant has discontinued the method, we will collect the date of discontinuation, reason(s) and current contraceptive method. If the survey is not completed within 7 days, the research staff will complete up to 3 attempts to contact the participant by each contact method for survey administration. No compensation for this call.

Twelve-month follow-up/Exit visit (Online link or Phone):* Twelve months after enrollment, participants will receive a link to a RedCAP survey to assess satisfaction with the implant and adverse events. If the participant has discontinued the method, we will collect the date of discontinuation, reason(s) and current contraceptive method. If the survey is not completed within 7 days, the research staff will complete up to 3 attempts to contact the participant by each contact method for survey administration. Participants will receive \$20 for this follow-up.

*Only the 1st 100 participants agreeing to longer-term study participation will be enrolled for the 3 to 12-month visits

Electronic Health Record Data Extraction: We will use PPAU electronic health records to identify all EC encounters that occurred during the study timeframe and will record all method choices at the time of EC provision or the follow-up visit, if UPA was administered and method initiation delayed. We will also review the Planned parenthood Association of Utah records for study participants in the 1-year following enrollment who were lost to follow-up to identify any care related to ENG implant removal, continuation, or pregnancy.

Data collection: Source documents for each participant and visit number will be completed by the study personnel at the time of the visit. Form development, data collection, and data management will occur in RedCAP, secure web platform for building and managing online databases and surveys. Source documents will be maintained in individual participant binders.

Data extraction will be recorded in a study specific REDCap database.

ENG implants will be supplied via Merck. Oral LNG EC is provided at no cost from PPAU and the study team will provide the other LARC (long acting reversible contraception) methods, the copper and LNG IUD, at no cost to avoid bias in LARC preference. All devices and the oral LNG EC are FDA approved and will be maintained in their usual packaging.

The investigator will be responsible for the destruction of the supplies at the study center pursuant to the ICH/GCP Guidelines, local regulations and the investigator's institutional policies. Clinical supplies will be received by a designated person at the study site, handled and stored safely and properly, and kept in a secured location to which only the investigator and designated assistants have access. The investigator will be responsible for keeping accurate records of the clinical supplies, the amount dispensed to and returned by the patients, and the disposition at the end of the study.

Procedures performed for research purposes only:

Study procedures involve women who present to Planned Parenthood for emergency contraception but who are also looking for long-acting reversible contraception at the same time as emergency contraception (EC).

Study procedures include:

Enrollment survey and choice of either a Nexplanon implant plus Plan B for emergency contraception or an IUD (either hormonal or copper) for EC and continued contraception.

Individuals who chose the Nexplanon implant plus Plan B will then be asked to provide pregnancy information at one month plus satisfaction surveys at 3, 6, 9, and 12 months.

Statistical Methods, Data Analysis and Interpretation

The investigator and study team will be responsible for analyzing the study data. The official clinical database in RedCAP will not be analyzed until medical/scientific review has been completed, protocol violations have been identified (if appropriate), and data has been declared complete.

Variables/Time Points of Interest

The primary outcomes are 1) pregnancy rate calculated as the proportion of women with a positive pregnancy test at 1 month following the enrollment and 2) proportion of EC clients willing to initiate a same-day contraceptive implant. Secondary outcomes will be implant continuation at 6 and 12 months and timing and reasons for discontinuation.

Statistical Methods

We will calculate the one-month pregnancy rate and confidence intervals will be constructed using effective sample size adjustments for the small sample size. We will report descriptive data on the methods chosen from all EC clients during the study timeframe, as well as the responses from the informational assessment on those not interested in an ongoing contraceptive method the same day. Kaplan-Meier estimates will be constructed to estimate the proportion of patients who continue with their implant for 1 year (continuation proportion) and to estimate the proportion that have an unintended pregnancy by 1 year.

Power/Sample Size:

This study seeks to obtain point estimates to evaluate guideline-adherent care and for future study evaluations/comparisons. Guidelines allow for same-day initiation of the ENG implant with oral LNG EC, with the unstudied assumption that pregnancy rates will be equivalent. With this assumption, we anticipate a 2.5% pregnancy rate (95% CI= 1.3-4.6) based on the Glasier article estimate of pregnancy rate in the upper BMI range (25-29.9) with use of oral LNG EC alone. [5] In our recent IUD EC trial the median BMI was 25. The potential exists for higher pregnancy rates in BMI >30, thus we will exclude this population and recommend oral UPA as the preferred EC if an IUD is not desired. Because additional episodes of UPI in the same menstrual cycle following EC increase risk of pregnancy, inclusion criteria include a recommendation to avoid UPI for 7 days after enrollment.

We plan for a sample size of a maximum of 300 participants for the primary outcome. This is based on the below table demonstrating the 95% CI and margin of error for sample size and upper limit CI of 5.0. We will analyze our pregnancy rate starting at 100 participants with 1-month pregnancy outcome data and with every subsequent 50 participants. We establish stopping rules demonstrating efficacy. For example, we will stop trial enrollment if the 1-month pregnancy point estimate is <2% AND the top end of the 95% CI is <5%. This would occur if 2 (or fewer) pregnancies occurred with 1-month pregnancy outcomes for 200 participants. This would yield a point estimate of 1% and a 95% CI (0-3.8%). There is not a perceived risk of having a 1-month pregnancy rate greater than what is known for oral LNG for EC. However, we have developed a stopping point if there is an unknown interaction or effect of combined use of oral LNG and ENG implant initiation. Once we have outcome data on 100 participants, we will cease trial enrollment if the point estimate for the 1-month pregnancy rate exceeds the known upper bound of the 95% CI for women with in the upper BMI range (25-29.9) using oral LNG EC (4.6, from Glasier estimate above).

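### Null hypothesis 1 runs in the same direction as clinical hypothesis 1, so neither rejecting nor retaining it supports the hoped-for conclusion, and the efficacy stopping rule uses a different limit

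*Combined protocol and SAP*

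**What the plan says.** Under Sample size, the first of two null hypotheses reads: "ENG implant along with oral LNG EC will not have a pregnancy rate greater than published oral LNG EC (2.5%; 95%CI 1.3-4.6"). The second is that same-day implant uptake will be lower than same-day IUD uptake.

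Under Clinical hypotheses, the first reads: "Combined oral LNG EC administration with same-day ENG implant insertion will not increase pregnancy rate point estimate compared to oral EC alone". The second expects clients who want a same-day LARC method to prefer the implant to IUDs.

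The background section commits to a comparison: "We propose to generate a baseline estimate and compare it with historical controls of oral LNG EC alone". Power/Sample Size describes the purpose as estimation: "This study seeks to obtain point estimates to evaluate guideline-adherent care and for future study evaluations/comparisons". Statistical Methods gives the analysis of the rate as an interval, not a test: "confidence intervals will be constructed using effective sample size adjustments for the small sample size".

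Power/Sample Size sets the looks: "We will analyze our pregnancy rate starting at 100 participants with 1-month pregnancy outcome data and with every subsequent 50 participants". The efficacy rule, introduced as an example, is: "we will stop trial enrollment if the 1-month pregnancy point estimate is <2% AND the top end of the 95% CI is <5" (per cent). Its illustration is: "This would occur if 2 (or fewer) pregnancies occurred with 1-month pregnancy outcomes for 200 participants", with an estimate of 1% and a 95% CI of 0-3.8%. A separate harm rule ends enrolment, once 100 participants have outcomes, if the point estimate exceeds 4.6%, the upper bound of the published interval.

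**The concern.** A null hypothesis is normally the statement the trial hopes to reject. Null 1 is instead the statement the trial hopes is true. Rejecting it would be a finding of harm. Retaining it could reflect a rate at or below 2.5%, or simply too few pregnancies to tell.

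Null 1 is the only null hypothesis stated for the comparison with published oral LNG EC. The risk lies in the report: a statement that null 1 was not rejected could be turned into a claim that the combination has no higher pregnancy rate than oral LNG EC alone. A favourable stop under the plan's own rule would not necessarily show that, because the rule is set at 5% and not at 2.5%.

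**Working it through.** **1. Direction of the hypotheses.** Let p be the one-month pregnancy rate.

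| | Null hypothesis | Clinical hypothesis | Relation |
|---|---|---|---|
| 1 | p not above 2.5% | no increase over oral EC alone | same direction |
| 2 | implant uptake below IUD uptake | implant preferred to IUD | opposed |

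The second pair follows the usual convention and the first departs from it. The only alternative to null 1 is p > 2.5%.

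**2. The plan's own figure.** For x = 2, n = 200, the Agresti-Coull interval adds z² = 1.96² = 3.84 to the sample size:
- adjusted n = 200 + 3.84 = 203.84
- adjusted proportion = (2 + 1.92)/203.84 = 0.0192
- half-width = 1.96 × √(0.0192 × 0.9808/203.84) = 0.0189
- interval = 0.04% to 3.81%

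This matches the stated 0-3.8%. The exact (Clopper-Pearson) interval is 0.12% to 3.57%. The plan does not name its method, so both are carried below.

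**3. The example against the three reference values.** The upper limit of 3.8% is below 5%, so the example meets the efficacy rule. It is below 4.6%, so it excludes the top of the published interval. It is above 2.5%, so it does not exclude rates above the reference in null 1.

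**4. All favourable stops.** Inputs: looks at 100, 150, 200, 250 and 300; favourable stop if the estimate is below 2% and the 95% upper limit is below 5%; the rule is taken to bind from the first look.

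| Method | Favourable stops and their 95% upper limits |
|---|---|
| Agresti-Coull | 0/100 4.44%; 1/150 4.06%; 2/200 3.81%; 3/200 4.52%; 4/250 4.19%; 5/300 3.96% |
| Exact | 0/100 3.62%; 1/150 3.66%; 2/150 4.73%; 3/200 4.32%; 4/250 4.05%; 5/300 3.85% |

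Every Agresti-Coull limit is below 4.6%. Every exact limit is too, except 2/150.

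**5. How the rule behaves.** These are exact binomial probabilities carried forward look by look, with the harm rule (estimate above 4.6%) applied at every look.

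| True rate | Efficacy rule met: Agresti-Coull | Efficacy rule met: exact |
|---|---|---|
| 1.0% | 94.5% | 95.1% |
| 2.0% | 56.7% | 60.0% |
| 2.5% | 36.3% | 40.1% |
| 4.6% | 2.8% | 4.1% |
| 5.0% | 1.6% | 2.5% |

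At a true 4.6% the harm rule stops about 71% of trials under either method. The efficacy rule therefore acts as a screen against rates of 5% or more. It is met in more than a third of trials when the true rate is exactly 2.5%, so meeting it says little about whether p lies above or below 2.5%.

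**6. Can an ending have an upper limit below 2.5%?** This depends on two things the plan leaves open: the interval method, and whether the rule binds before 200.
- Binding from 100: the lowest upper limit is 3.62% (exact) or 3.81% (Agresti-Coull). Jeffreys limits would give 2.47% at 0/100, although that method does not reproduce the plan's 3.8% (it gives 3.17% for 2/200).
- Binding from 150: 0/150 gives 2.43% (exact) or 3.00% (Agresti-Coull).
- Binding from 200: 0/200 gives 1.83% (exact) or 2.27% (Agresti-Coull). This ending has probability 0.99²⁰⁰ = 13.4% at a true 1% and 0.975²⁰⁰ = 0.6% at a true 2.5%.

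**The case against.** The strongest reply is that this is an estimation study. Primary objective 1 is a point estimate, clinical hypothesis 1 is itself worded about the point estimate, and the analysis is a rate with an interval. No test, significance level or power is given for null 1, so no planned analysis can yield a non-rejection. The published 2.5% is uncertain (1.3-4.6), favourable stops mostly exclude 4.6%, and the harm rule guards against a materially higher rate.

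Most of this stands. It confines the problem to what is stated and what may be claimed; the design and the estimate are unaffected. It does not rescue null 1: an estimation study needs no null hypothesis, and a descriptive comparison should be labelled as one.

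A reader might infer two stronger points that the documents do not support.
- That no favourable ending could ever show a rate below 2.5%. This turns on the interval method and on when the rule binds. The plan introduces the rule as an example and illustrates it only at 200.
- That the trial is underpowered for null 1, judged by a single test at 300 participants. Such a test is not part of the design and ignores both stopping rules.

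**Conclusion.** The point holds as one of wording and interpretation. Null 1 and clinical hypothesis 1 run the same way, so neither outcome of a test of null 1 would support the hoped-for conclusion. The efficacy rule answers a different question, whether 5% or more can be excluded, and the plan's example of 2/200 with an upper limit of 3.8% does not exclude rates above 2.5%.

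It would be wrong to conclude that a planned p-value, the sample size or the estimate is in error. The point estimate remains valid and may be set beside 2.5% descriptively. The direction of null 1 and the 2/200 example rest on the text and on the plan's own figure. The probabilities assume looks at 100 to 300 in steps of 50, both stopping rules applied at every look, and Agresti-Coull or exact limits.

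The sponsor should correct this, since the correction is cheap and governs what a favourable ending may be said to show.

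**What to change.** Preferred:
- Delete null 1 and state primary objective 1 as estimation of the one-month pregnancy rate with a 95% CI.
- Label the comparison with published oral LNG EC (2.5%, 1.3-4.6) as descriptive.
- Word a favourable result as excluding a one-month rate at or above the observed upper limit. Reserve any claim of a rate no greater than oral LNG EC for an upper limit below 2.5%.

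Alternative, if a hypothesis is kept: make it agree with the stopping rule, with H0: p ≥ 5% against H1: p < 5%. Justify the 5%, and define success as the full existing rule (estimate below 2% and 95% upper limit below 5%). At a true 5% that rule is met in 1.6% of trials with Agresti-Coull limits or 2.5% with exact limits, so the interval method has to be named in advance.

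Cost: the preferred fix changes wording only, adds no participants and leaves the looks as they are, but the stated claim becomes less favourable. The alternative also requires the sponsor to defend 5%, which is twice the 2.5% reference.

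### The promised comparison with published oral LNG alone has no interval that carries both sampling errors, and not rejecting a 'not greater' null cannot support it

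*Combined protocol and SAP*

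**What the plan says.** All references are to the combined protocol and SAP.

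- **Background:** "We propose to generate a baseline estimate and compare it with historical controls of oral LNG EC alone".
- **Sample size, null hypothesis 1:** "ENG implant along with oral LNG EC will not have a pregnancy rate greater than published oral LNG EC (2.5%; 95%CI 1.3-4.6".
- **Clinical hypotheses:** the combination "will not increase pregnancy rate point estimate compared to oral EC alone".
- **Statistical Methods:** "We will calculate the one-month pregnancy rate and confidence intervals will be constructed using effective sample size adjustments for the small sample size". No difference, ratio, test or margin is given for the comparison.
- **Power/Sample Size:** "we anticipate a 2.5% pregnancy rate (95% CI= 1.3-4.6", taken from the published subgroup with BMI 25-29.9. The aim is put as "This study seeks to obtain point estimates to evaluate guideline-adherent care and for future study evaluations/comparisons". On numbers: "We plan for a sample size of a maximum of 300 participants for the primary outcome", and "We will analyze our pregnancy rate starting at 100 participants with 1-month pregnancy outcome data and with every subsequent 50 participants". The efficacy stop needs a point estimate below 2% with an upper 95% limit below 5%, illustrated by 2 or fewer pregnancies in 200 (1%, 95% CI 0-3.8%). The high-side stop uses 4.6%, the upper limit of the published interval.

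**The concern.** The plan commits to a comparison and gives no analysis for it. Two sampling errors are involved, the study's and the published study's, and neither is carried into a comparative estimate. The clinical hypothesis, taken literally, is settled by which point estimate is lower. Null hypothesis 1 puts the desired conclusion in the null, where a small study with few events will usually leave it unrejected whatever the truth.

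At stake is the sentence clinicians will take away. A result such as 7/300 (2.33%, below 2.5%) could be reported as no increase over oral LNG alone, although the data would be compatible with roughly double the published rate.

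**Working it through.** **Inputs.** Published rate 2.5% with limits 1.3 and 4.6 (Sample size; Power/Sample Size). Efficacy example 2/200 with CI 0-3.8%, maximum 300, looks at 100, 150, 200, 250 and 300 (Power/Sample Size). The 7/300 result is my illustration: the largest count at 300 whose point estimate is below 2.5%.

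**1. Reproduce the plan's interval.** Agresti-Coull for 2/200, with z = 1.96:
- adjusted n = 200 + 3.84 = 203.84; adjusted rate = (2 + 1.92)/203.84 = 0.01923
- half-width = 1.96 × √(0.01923 × 0.98077/203.84) = 0.01885
- limits 0.04% to 3.81%, matching the stated 0-3.8%. Wilson gives 0.27 to 3.57.

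**2. Treat 2.5% as fixed.** At 2/200 the upper limit for the difference is 3.81 - 2.5 = +1.31 points (Wilson +1.07). An increase is not excluded even on this most lenient reading.

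**3. Can any efficacy stop exclude an increase?** With Agresti-Coull limits, the rule (estimate below 2%, upper limit below 5%) is met by at most 0/100, 1/150, 3/200, 4/250 or 5/300. A trial that continues past one look therefore carries at least 1, 2, 4 or 5 pregnancies into the next. The results that can trigger the stop, with upper limits, are:

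| Result | Upper limit, % |
|---|---|
| 0/100 | 4.44 |
| 1/150 | about 4.1 |
| 2/200 | 3.81 |
| 3/200 | 4.52 |
| 4/250 | 4.19 |
| 5/300 | 3.96 |

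The lowest is 3.81%, the plan's own example. None is below 2.5%.

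**4. Include the published interval (MOVER).** Let p, l, u be the study's estimate and limits, and 2.5, 1.3, 4.6 the published ones, all in percent:
- lower = (p - 2.5) - √[(p - l)² + (4.6 - 2.5)²]
- upper = (p - 2.5) + √[(u - p)² + (2.5 - 1.3)²]

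For 2/200 (Agresti-Coull):
- upper = -1.5 + √(2.81² + 1.2²) = -1.5 + 3.05 = +1.55
- lower = -1.5 - √(0.96² + 2.1²) = -1.5 - 2.31 = -3.81

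For 7/300 (Agresti-Coull limits 1.04 to 4.83):
- upper = -0.167 + √(2.50² + 1.2²) = +2.61
- lower = -0.167 - √(1.29² + 2.1²) = -2.63

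| Result | Limits used | Difference | 2.5% fixed | Published CI included |
|---|---|---|---|---|
| 2/200 | Agresti-Coull | -1.50 | -2.46 to +1.31 | -3.81 to +1.55 |
| 2/200 | Wilson | -1.50 | -2.23 to +1.07 | -3.72 to +1.34 |
| 7/300 | Agresti-Coull | -0.17 | -1.46 to +2.33 | -2.63 to +2.61 |
| 7/300 | Wilson | -0.17 | -1.37 to +2.24 | -2.58 to +2.52 |

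The same construction on the log scale with Wilson limits gives a ratio of 0.40 (0.10 to 1.67) for 2/200 and 0.93 (0.36 to 2.45) for 7/300.

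**5. What the published error adds.** Total width at 2/200 (Agresti-Coull) goes from 1.31 + 2.46 = 3.77 to 1.55 + 3.81 = 5.36 points, a factor of 1.42. At 7/300 it goes from 3.79 to 5.24, a factor of 1.38. The upper limit rises by 0.24 and 0.28 points (0.27 and 0.28 with Wilson).

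**The case against.** The best defence is that the study is descriptive. Its first primary objective is a point estimate, the Power/Sample Size section says the same, and no powered test is claimed. The single-arm interval is right for that purpose, and its worked example reproduces. A reader could set the study's rate and interval beside the published rate and interval and judge for themselves. This stands as far as it goes: a purely descriptive report would be consistent with the stated aim. It does not remove the comparison that the Background promises and that the hypotheses state.

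Three stronger readings are tempting and are not supported.

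- *That the plan treats 2.5% as exact.* It never says so. It quotes the 1.3-4.6 interval beside the figure twice and uses the upper limit in the high-side stopping rule.
- *That the planned error bars are too narrow.* The only planned interval is for the study's own rate. No comparative interval exists that could be too narrow; the gap is that none is specified.
- *That about half of the uncertainty is ignored.* The upper limit decides 'not greater'. There the published error supplies 1.2² = 1.44 of 2.81² + 1.2² = 9.34, or 15%, at 2/200, and 1.44 of 7.69, or 19%, at 7/300 (Agresti-Coull). In neither case does including it change the conclusion.

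The high-side stop is a separate rule on a point estimate. A comparative interval would not alter how it behaves, so it is no evidence for this point.

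**Conclusion.** The point holds in this form: the comparison with oral LNG alone is promised and stated as a hypothesis, no analysis is specified for it, and 'not greater' could not be supported as planned. The main reasons are the width of the study's own interval, the absence of a margin, and the placing of 'not greater' as the null. The uncertainty of the published rate is a real but secondary contributor. Its larger effect is on the lower side of the interval, and so on any claim of a reduction or of equivalence.

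In size, the plan's efficacy example leaves an increase of about 1.3 to 1.6 points open, and 7/300 leaves about 2.5 to 2.6 points open, which is as large as the published rate itself.

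Assumptions: the two estimates are independent; the intervals are not adjusted for repeated looks; the efficacy rule is applied at every look and the result is read at the look that triggers it; and the comparison carries sampling error only. It does not account for differences between the enrolled population (BMI below 30) and the published subgroup (BMI 25-29.9), nor for the lack of concurrent controls. The sample-size table that the Power/Sample Size section refers to is not in the text I had, so I did not check it.

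**What to change.** 1. In Statistical Methods, pre-specify the difference and the ratio of the one-month pregnancy rate against the published rate, each with a 95% interval that combines both sampling errors. MOVER with the published limits 1.3 and 4.6 does this without needing the published counts. Name the single-arm interval method; Agresti-Coull matches the worked example.
2. State that any conclusion on hypothesis 1 rests on that interval, not on the order of the point estimates or on a non-rejected null. Bring the clinical hypothesis into line.
3. Report the size of increase not excluded, for example: difference -0.2 points, with an increase of up to 2.6 points not excluded.
4. If a formal claim of no increase is wanted, name a margin in advance and make an increase of at least that margin the null. Otherwise label the comparison descriptive.

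The cost is one extra calculation and some SAP wording, with no change to participants, visits or stopping rules. The small downside is that the comparative statement will read less favourably than a bare comparison of two percentages.
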